The first meeting is an information interview with one of the doctors responsible for the trial. Here, the subject will be informed orally and given written information. The person in question has the right to bring along an assistant. The meeting will take place in quiet undisturbed locations with time for questions. The information itself deals with the experiment and its advantages and disadvantages and must be easily understood by the subject.

The subject is informed about the right to refuse information about significant health conditions. The informing doctor is responsible for ensuring that the information is understood. The subject then has the right to a minimum of one-week reflection time.

On the screening day, written consent is obtained from the subject. At the declaration of consent, the investigator of the trial notes that written and oral information is given as stated above.

The subjects are informed that they may withdraw their commitment to participate in the trial at any time without this having any effect on current or subsequent treatment or controls.

The subject is informed if, in the course of the experiment, significant information about his or her health condition arises he/she will be informed of this, unless the subject explicitly states that he does not want this information.

Results

When the results of the study are available, one of the project's doctors will if possible inform the participating subjects about the result. Information on the participating subjects are protected under the *Act on processing of personal data* and the *Law on patients' rights* .

Side effects and risks

Sterile disposable catheterization and UPR and AAR measurement results in immediate discrete discomfort during measurement and minimal risk of developing cystitis, which is minimized by sterile technique.

The side effects of imipramine are well known (12) . The known side effects of imipramine are available in the Summary of Product Characteristics 4.8.

The psychiatric and cardiac side effects are considered irrelevant in relation to a single dose. Possible adverse reactions are expected to primarily be anticholinergic (e.g. dry mouth, dizziness, and hypotension) and hypersensitivity reactions such as rash and urticaria.

Pregnancy

Imipramine does not appear to be associated with an increased risk of malformations (25–27). There is a risk of withdrawal symptoms associated with delivery. The subjects are screened for pregnancy with pregnancy test (urine) prior to both test days. Only single-dose low dose (50 mg) imipramine is given. It is therefore assessed that there is no risk if pregnancy occurs immediately after the trial day, since the concentration of the drug is reduced to approx. 6- 40% (half-life 6-18 hours) of the dose and because maximum dose is already low, and as the substance has not been shown to be teratogenic in spite of the high usage for many years.

Pros and cons

Disadvantages: Possible side effects of the study drug (though low dose and single dose), low risk of cystitis associated with UPR (minimized by sterile technique), and discomfort associated with UPR and AAR (transient nuisance) .

Advantages: The subjects will have no immediate advantage by participating in this trial. The participants contribute to the gathering of useful new knowledge about the effect of the trial drug on the pressure in the urethra and the anal canal. This can be beneficial for future patients with stress urinary incontinence and fecal incontinence.

Adverse Events

All Adverse Events are registered on the CRF at the following times:

- At the end of trial day 1 and trial day 2.
- At the start of the trial day 2 (AEs since trial day 1).
- Five days (corresponding to > 5 half-lives) after the last test day (contact by phone).

Any SAE (Serious Adverse Events), is immediately (within 24 hours) reported to the sponsor ([name]) according to the SOP for this. All AEs are followed until they are completed - also beyond the duration of the trial. AE is terminated when the subject is in normal health or stable condition. All AE, Adverse Drug Reactions (ADR), Serious Adverse Reactions (SAR), Serious Adverse Events (SAE) and Suspected Unexpected Serious Adverse Reactions (SUSAR) are handled in accordance with ICH-GCP and applicable legislation (from the Danish Medicines Agency):

"The sponsor must immediately notify the Danish Medicines Agency if, during the trial, unexpected and serious suspected adverse reactions (Suspected Unexpected Serious Adverse Reactions , SUSARs) are observed, cf. 2. No. 1.

The definitions are as follows, cf. the Executive Order on clinical trials:

- *incident: any undesirable event in a patient or subject in a clinical trial after treatment with a drug, without necessarily being related to this treatment and the adverse event*
- *side effect: any harmful and undesirable reaction to a test drug regardless of dose*
- *Unexpected side effect: an adverse reaction whose nature or severity does not correspond to the product information (eg, the Investigators- Brochure for an unapproved test drug or the SPC, in the case of an approved product)*
- *Serious event or serious side effect: An event or side effect, which, regardless of dose, results in death, is life-threatening, involves hospitalization or hospitalization, results in significant or persistent disability or incapacity for work or leads to congenital anomaly or malformation.*

Reference is made to the guideline in the area:

Guideline for reporting adverse reactions arising from clinical trials (Detailed guidance on collection , verification and presentation of adverse event / reaction reports arising from clinical trials on medicinal products for human use (CT 3)). These guidelines can be found on the Commission website under "Volume 10".

Sponsor's obligations

Pursuant to section 89 (1) of the Danish Medicines Act. 2, no. 1, the sponsor must immediately notify the Danish Medicines Agency if there are unexpected and serious suspected adverse reactions during the trial.

The sponsor must ensure that any information on unexpected and serious suspected adverse reactions (SUSAR) that is fatal or life-threatening is recorded and reported to the Drug Administration as soon as possible and within 7 days of the knowledge of such a suspected adverse reaction.

Within 8 days of the report, the sponsor must notify the Danish Medicines Agency of all relevant information about the sponsor's and investigator's follow-up to the report.

All other unexpected and serious suspected adverse reactions must be reported to the Danish Medicines Agency no later than 15 days after the sponsor has been informed of these.

Any report must be accompanied by comments on any implications for the trial.

(...)

All adverse reactions and events are reported at the end of the trial in the final report to the Danish Medicines Agency.

Investigator's obligations

Furthermore, the investigator has the following obligations, cf. the Order for Clinical Trials: Investigator must immediately report any serious incidents to the sponsor, with the exception of the serious events identified in the trial protocol or investigator brochure as events that do not require immediate reporting.

The report must be followed up by a detailed written report, and in both the immediate reporting and in the subsequent report, the investigator must identify the subjects with a personal code number.

Investigator must also report to the sponsor events and / or abnormal analysis results that are stated as critical to the safety of the subjects in the trial protocol.

The alert must be in accordance with the rules and deadlines set out in the Protocol. When reporting deaths, the investigator must provide any additional information requested by the sponsor.

The Sponsor / Sponsor Investigator is required to report any suspected serious or unexpected adverse drug reactions.

In order for a side effect to meet the reporting requirement, the side effect must be serious, ie. resulting in death, life-threatening, hospitalization or prolongation of hospitalization, resulting in significant or persistent disability or incapacity or leading to congenital anomaly or malformation.

In addition, the side effect must be related to the test drug. In other words, it would say that it is supposed to be a causal link between the intake of the drug and the side effect that has occurred.

Both investigator and sponsor (or sponsor investigator) must assess causality.

The sponsor must not, therefore, disclose the investigator's assessment, why reports where the sponsor does not agree with the investigator should still be reported.

The side effect should be unexpected, which is a side effect whose nature or severity does not match the product information (eg Investigators Brochure for an unapproved test drug or the SPC if it is an approved drug).

If the serious side effect is not listed in this product information, it is considered unexpected.

In the case of a blinded trial, the assessment of the adverse reaction must be made before blinding. From blinded trial, all SUSAR then unblinded before reporting to the authorities.

Follow-up reports (follow up) should only be submitted if applicable. What information is relevant or not should be based on a medical and scientific assessment. "

Reference document

The reference document for imipramine is the Summary of Product Characteristics for Imipramine "DAK".

Annual report

As the trial lasts for less than 1 year, no annual report is submitted, but at the end of the trial, the final report is submitted in accordance with applicable legislation. From the Danish Medicines Agency:

"After the end of the trial, the sponsor must, within 90 days of the end of the trial, inform the Danish Medicines Agency that the trial has been completed by Schedule for completion of clinical trials . (...)

As soon as possible and no later than 1 year thereafter, the test result must be entered in EudraCT. The data will then be published on www.clinicaltrialsregister.eu. This replaces that the trial result must be submitted to us [the Danish Medicines Agency]. You can see more [here](#) how to enter the results in EudraCT . As data becomes publicly available, there will in future not be a requirement to submit a publication to us. (...)

Medical charts

Only healthy subjects are recruited for the trial, and therefore no records will be created or will be recorded during the study. CRF is documented instead.

Unblinding

Participants' study medication is always unblinded if SUSAR occurs. If other adverse events occur, the investigator or treating doctor will decide if unblinding is needed. Unblinding is done by the investigator (or subinvestigator): They open the envelope with the number corresponding to the subject's randomization number (stored envelopes are locked in the phase-1 unit where the experiment takes place). The envelopes contain information about the given test drug; whether placebo is given day 1 or day 2 and if there is given imipramine day 1 or day 2. Sponsor is informed of unblinding by person or telephone.

Drop out

In case of drop out, the reason must be registered on the CRF. If the cause is AE, this is followed until AE is complete - beyond the duration of the trial. AE is complete when the patient is in normal health again or the condition is stable.

As a rule, there is not unblinding on drop out, unless the cause for drop out is one of the situations specified in the section "Unblinding". All subject that drop out are offered a telephone call 5 days after intake of trial medication to detect any AE.

Data from drop out is not analyzed, as the analysis is performed as balanced crossover study (see statistics section). We recruit and therefore include trial subjects until a total of 16 participants have completed the trial, ie. both trial day 1 and trial day 2. When recruiting subjects after the first 16, calls are made to Region Hovedstadens Apotek in relation to which medicine kit the next subject must consume; to preserve the balanced design and to maintain blinding.

Data

On screening day, personal data, incl. CPR number, inclusion and exclusion criteria, medical history and any findings by objective examination on Case Report Form (CRF) made for this purpose. On trial day 1 and trial day 2, the date, results of the pregnancy test, subject ID, time for the intake of tablets, and time for UPR - and AAR measurements, and any AE. Data from the UPR measurement is electronic and transferred to encrypted USB key and from there to the data logged folder according to the approval of the Data Protection Agency.

Data storage

Data from UPR and AAR up are kept in anonymous form on PC, to which only the data-processing personal have access. All files are placed in a locked cabinet, to which only the data controller has access. Data is stored for 5 years, after which data is deleted. Envelopes with data on blinded medicine are delivered from Region Hovedstadens Apotek together with the medicine kits and stored together with Trial Master File and CRF locked in office at Zelo Phase-1 Unit.

Data controllers & data processors

Primary data manager and data processor: Chief physician, dr. med. [name], Department of Gynecological-Obstetrics, Herlev and Gentofte Hospital.

Secondary data processor: Doctor [name], Department of Clinical Pharmacology, Bispebjerg Hospital.

Financing

The trial is funded by the Department of Clinical Pharmacology's research funds.

Budget

	Price
Subject reimbursements	3,000 DKK * 16 subjects = 48,000 DKK
Manufacture and packaging of medicine	11,000 DKK in starting fee 300 DKK * 20 medicine kit = 6,000 DKK Total 17,000 DKK
Application to The Danish Medicines Agency	7,734 DKK
Total	72,734 DKK

Administrative conditions

The study is performed according to current legislation and ICH-GCP. The study must be approved by the Danish Medicines Agency, the Regional Science Ethics Committee and the Data Protection Agency. The study is monitored by the GCP.

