- Known hypersensitivity to imipramine.
- history of significant cardiovascular, gastrointestinal, endocrinologic, haematologic, immunological, metabolic or genitourological disease (incl. surgery after pelvic trauma, urethral hypermobility or prolapse of the organs of the pelvis), pulmonary disease, neurological disease, dermatological disease, psychiatric disease, kidney disease, malignant disease and / or other major diseases assessed by the investigator.
- History of or symptoms of urinary incontinence.
- Treatment of infection at least one week before trial day 1, ie. fever or symptoms of viral infection, bacterial infection (including upper respiratory tract infection) or fungal infection (not cutaneous).
- Clinically significant findings assessed on clinical study on screening day.
- Pregnant.
- Pulse <40 or > 100 beats per minute. Mean systolic blood pressure > 140 mmHg or mean diastolic blood pressure > 90 mmHg (average of 3 measurements on screening day). If blood pressure or heart rate differs from this, an additional 3 measurements can be performed.
- Prescription drugs or over-the-counter or natural remedies at least 2 weeks before trial day 1 and trial day 2. Exclusive paracetamol up to 2 g / day and exclusive contraception.
- Smoking 3 months before trial day 1 and trial day 2.
- Alcohol consumption, ie. > 14 drinks per week within 3 months before the trial day 1 and experimental day 2.
- Substance abuse within 3 months before trial day 1 and trial day 2.
- Any condition that allows the investigator not to include the subject.

Recruitment

Healthy volunteers from previous UPR trials in Zelo Phase-1 unit, which have expressed interest in participating in future UPR studies will be informed about the trial and have the opportunity to contact us for inclusion. If there are not recruited enough subjects this way, we will recruit with advertisement on www.forsøgsperson.dk. All recruitment - and the information - must be approved by the Regional Research Ethics Committee.

Reimbursement

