Allowance of DKK 125 per hour and DKK 1000 in nuisance bonus for the UPR measurements and AAR measurements on trial day 1 and trial day 2. Thus, compensation of DKK 250 is granted for information day and screening day (approximately 2 hours), DKK 1375 for trial day 1 (3 hours and 1000 DKK nuisance bonus) and 1375 DKK for trial day 2 (3 hours and 1000 DKK nuisance bonus). A total of DKK 3000 in allowance if the entire trial is carried out. The reimbursement must also be authorized by the Regional Research Ethics Committee.

Procedures

Information day: Subjects receive written and oral information about the trial. The subject is entitled to an assessor. Total approx. 30 minutes duration. The subject is offered reflection time, but if the subject is ready to sign written consent, the next part is done immediately.

Screening day: Written consent is obtained. An objective examination is carried out and the medical history and information about the consumption of medicine incl. herbal remedies and supplements are obtained. Objective examination by doctor. Blood pressure x3 is measured after 5 minutes of rest in a supine position. Total approx. 1 hour duration.

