Trial day 1: Pregnancy is excluded by pregnancy test via urine sample. The subject is randomized to one of the 16 prefabricated, blinded medicine kits. The subject's bladder is emptied by sterile disposable catheterization and then 150 ml of 9% NaCl are instilled the bladder. UPR is performed with 10 measurements, while the subject is relaxing the pelvic floor. Then 5 measurements while the subject is squeezing the pelvic floor. Measurements in the urethra are followed by measurements in the anal canal, where also 10 measurements are made while the subject is relaxed, and 5 measurements while the subject squeeze in the pelvic floor. The subject consumes two tablets according to the randomization and trial day. This will be either two placebo tablets or two tablets of Imipramin DAK 25 mg. The subject relaxes for 1 hour. Again, the bladder is emptied by sterile disposable catheterization and then the bladder is filled with 150 ml of 9% NaCl followed by UPR with 10 measurements, while the subject relaxes the pelvic floor, then 5 measurements while the subject squeezes the pelvic floor. The measurements in the urethra are followed by measurements in the anal canal, where also 10 measurements are made while the subject is relaxed, and 5 measurements while the subject is squeezing the pelvic floor. After that, any AE and ADR are registered. Total approx. 3 hours duration.

Trial day 2 : Minimum 1 week after trial day 1 to ensure elimination of the drug. Procedure is identical to trial day 1. Total approx. 3 hours duration.

A total of 4 days of total approx. 8 hours duration.

Methods

UPR

UPR is a validated method for simultaneously measuring the pressure ratio and the cross-sectional area of the urethra. A very thin and very flexible polyurethane bag is introduced into the urethra. Sound waves measure the cross-sectional area of the urethra while pumping air into the polyurethane bag, thereby providing knowledge of the pressure in the urethra. The opening and closing pressure, opening and closing elasticity and the hysteresis can thus be measured by UPR. UPR is more reproducible, with lower variability (and therefore greater statistical power), compared to UPP (20,21). No risk or complication of the procedure has been demonstrated beyond limited discomfort by catheter insertion and a minor risk of cystitis, which, however, is minimized by sterile technique.

AAR

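### Hypotension is an expected reaction, but no blood pressure or pulse reading is planned on either dosing day, so a fall without symptoms would go unrecorded

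*Combined protocol and SAP*

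**What the plan says.** All places are in the combined protocol and SAP.

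- **Side effects and risks.** Of the reactions to a single dose it states: "Possible adverse reactions are expected to primarily be anticholinergic (e.g. dry mouth, dizziness, and hypotension". Hypersensitivity reactions are named alongside. The sentence before it sets psychiatric and cardiac side effects aside as irrelevant to a single dose.
- **Procedures, screening day.** "Blood pressure x3 is measured after 5 minutes of rest in a supine position". This is the only blood pressure measurement in the Procedures section.
- **Exclusion criteria** (printed under a second Inclusion criteria heading). The numeric pressure limits are upper limits: "Mean systolic blood pressure > 140 mmHg or mean diastolic blood pressure > 90 mmHg (average of 3 measurements on screening day". The pulse limits in the same bullet run both ways: "Pulse <40 or > 100 beats per minute". A discretionary criterion also applies: "Clinically significant findings assessed on clinical study on screening day". The list closes with a general investigator-judgement criterion.
- **Procedures, trial day 1.** The sequence is pregnancy test, kit assignment, catheterization and filling, UPR, AAR, tablets, one hour of rest, catheterization and filling, UPR, AAR. It ends: "After that, any AE and ADR are registered. Total approx. 3 hours duration". Trial day 2 follows the same procedure.
- **Data.** Trial-day items are the date, pregnancy test result, subject ID, "time for the intake of tablets, and time for UPR - and AAR measurements, and any AE".
- **Adverse Events.** Events are recorded at the end of each trial day, at the start of trial day 2, and by telephone five days after the last trial day.

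**The concern.** Of the three anticholinergic examples the plan gives, dry mouth and dizziness are things a subject can report. Hypotension is defined by a measurement, and the plan schedules that measurement only before any drug is given.

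Two things are at stake, both about safety information:

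- A fall in pressure that causes no symptoms leaves no trace in the data, on imipramine or on placebo.
- If a subject reports dizziness, also an expected reaction, there is no planned trial-day reading, before or after dosing, to show whether pressure had fallen.

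The primary urethral endpoint and the exploratory anal measurements are not at stake.

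**Working it through.** **1. Where blood pressure or pulse appears**

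| Part of the plan | Blood pressure or pulse? |
|---|---|
| Screening day | Three pressure readings, supine; upper limits for pressure, two-sided limits for pulse |
| Trial day 1, before tablets | None listed |
| Trial day 1, after tablets | None listed |
| Trial day 2, before and after tablets | None listed (same procedure) |
| Trial-day data items | None listed |

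Post-dose readings are therefore planned on 0 of 2 dosing days, which is 0 of 16 × 2 = 32 subject-days among completers.

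**2. Can the screening reading stand in?**

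The Design section allows screening and trial day 1 to share a day, so the screening reading can serve as a same-day pre-dose value for trial day 1. It can never be a post-dose value. Eight of the 16 kits give imipramine on trial day 2, at least 7 days after trial day 1. For those women the only planned reading is at least 7 days old when they take the active drug.

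**3. The plan's own residual-drug figure**

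The Pregnancy section gives about 6–40% remaining after the trial day, for a half-life of 6–18 hours. With first-order decay, fraction remaining = 0.5^(t / half-life). At t = 24 h:

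- half-life 6 h: 0.5^(24/6) = 0.0625, or 6%
- half-life 18 h: 0.5^(24/18) = 0.397, or 40%

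The figure reproduces at 24 hours, so the same formula is used below.

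**4. Concentration when the subject leaves**

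Inputs from the plan: peak within 1 hour and half-life 6–18 hours (Imipramine - pharmacokinetics); visit of about 3 hours with 1 hour of rest after the tablets (Procedures). The departure time is not given. The visit less the rest leaves 3 − 1 = 2 hours for pre-dose and post-dose work together. How that splits is an assumption, varied here. The peak is taken at 1 hour, and decay at the elimination half-life is assumed from then on.

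| Pre-dose work (assumed) | Leaves after intake | Time after peak | Half-life 6 h | Half-life 18 h |
|---|---|---|---|---|
| 0.5 h | 2.5 h | 1.5 h | 0.5^(1.5/6) = 84% | 0.5^(1.5/18) = 94% |
| 1.0 h | 2.0 h | 1.0 h | 0.5^(1/6) = 89% | 0.5^(1/18) = 96% |
| 1.5 h | 1.5 h | 0.5 h | 0.5^(0.5/6) = 94% | 0.5^(0.5/18) = 98% |

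The range is 84% to 98% of peak. It describes exposure at departure. It does not give the frequency or size of any fall in pressure, for which the plan has no figure.

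**5. What the remaining safety contacts can catch**

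End-of-day registration catches what the subject reports or staff observe before she leaves. The next planned contact is at least 7 days later after trial day 1, and 5 days later after trial day 2. Neither involves a planned pressure reading.

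**The case against.** The strongest reply is that nothing here is a contradiction in the strict sense. The plan calls hypotension a possible reaction, promises no monitoring for it, stresses the low single dose, and enrols healthy women seen by a doctor at screening. Its eligibility, procedure and data sections agree with one another. That stands: this is a gap between a stated expectation and what is measured. It does not remove the gap, because hypotension is named directly after cardiac effects are set aside.

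Four stronger readings are tempting and are not supported:

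- *Subjects go home with no safety check.* Adverse events and reactions are registered at the end of each trial day, so symptomatic hypotension can be captured. Only the pressure reading is absent.
- *Only high pressure can exclude.* That is true of the numeric limits. The investigator sees three readings and can exclude on clinically significant findings or on judgement.
- *The adverse event comparison with placebo will be biased.* No such comparison is planned. Results presentation covers baseline characteristics, UPR and AAR, and the Summary leaves side effects to further studies. Adverse reactions and events are only to be listed in the final report.
- *Subjects lie down for the hour and then stand up to leave.* The trial-day text says only that the subject relaxes; no posture is stated.

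**Conclusion.** The point holds in a limited form. The plan expects hypotension but schedules no blood pressure or pulse reading on either dosing day, so a symptomless fall would go unrecorded and dizziness could not be related to pressure. On the assumption that subjects leave 1.5 to 2.5 hours after intake, and that decay runs at the elimination half-life from a peak at 1 hour, they do so with about 84% to 98% of peak concentration remaining.

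The gap concerns participant safety and the completeness of the safety description. It does not touch the urethral or anal pressure results, and it biases no planned test. It is worth correcting because the correction is cheap. The conclusion assumes that the published procedure and data sections are complete on this point.

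**What to change.** Reconcile the expected-reaction statement in Side effects and risks with the trial-day procedure and the Data section.

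- If the sponsor does not in fact expect hypotension after this single dose, the statement should say so and give the reason.
- If hypotension stays listed, add blood pressure and pulse to the procedure and the CRF on both trial days: once before dosing, and once after the last AAR measurement so that neither endpoint is disturbed. Report the values descriptively by treatment alongside the adverse events, with no formal test.

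Body position, any lower eligibility limit and any criterion for leaving are for the sponsor's clinicians; none is proposed here.

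Cost (this review's estimate): a few minutes per trial day, using a measurement already made at screening, and two CRF lines. Sample size, randomization and the UPR and AAR analyses do not change.
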